4.5 Treatment compliance

Records of study drug used, doses, and intervals between visits will be kept during the study. Where appropriate, patients will receive treatment with study drug as outpatients. Patients will be asked to record any symptoms experienced as well as other medications taken. Dosing information for SGN-35 must be documented. Any change of dose, missed doses or dose interruptions must be recorded.

4.6 Visit schedule and assessments

4.6.1 Visit and assessment schedule (see next page)

Evaluations

Pretreatment (Screening)

- Complete medical history including transfusion history in prior 12 weeks
- Prior and current medication list
- Physical exam with spleen measurement
- ECOG performance status
- Vital signs (temperature, heart rate, breathing rate, blood pressure, height, weight)
- 12 lead ECG

A study of brentuximab vedotin (SGN-35) in CD30-positive systemic mastocytosis with or without an associated hematological clonal non-mast cell lineage disease (AHNMD)

- Magnetic resonance imaging (MRI) or computed tomography (CT) scan of the abdomen/pelvis with and without contrast including 3D spleen and liver volumes
- Bone marrow aspirate and biopsy with cytogenetics, flow cytometry, *KIT* mutation status
- Chest x-ray (2 views PA and lateral)
- MPN-SAF modified for mast cell symptoms
- Hematology, chemistries/liver function tests, serum tryptase, PT, PTT (**Please refer to section 4.8.1 for detailed lab evaluations**)
- Pregnancy test (women of child bearing potential)

Day 1 of Cycles 1 to 8 (+/- 3 days):

- Evaluate for adverse events
- Interval medical history including transfusion history
- Physical exam, including measurement of your spleen, weight, and vital signs
- Current medications
- ECOG performance status
- MPN-SAF modified for mast cell symptoms
- Hematology, chemistries/liver function tests (with phosphorus on Cycle 1 Day 1 only), serum tryptase, PT, PTT (**Please refer to section 4.8.1 for detailed lab evaluations**)
- Pregnancy test (women of child bearing potential)
- Drug infusion
- Response assessment per IWG-MRT-ECNM criteria (starts Cycle 2 Day 1)

For Cycle 5 Day 1 (End of cycle 4) also need to complete the following:

- MRI or a CT scan of the abdomen/pelvis with and without contrast including 3D spleen and liver volumes
- Chest X-ray-2 views PA and lateral (only if disease-related finding(s) were found at baseline)
- Bone marrow aspirate and biopsy with cytogenetics, flow cytometry, *KIT* mutation status

Phosphorus will be additionally done on Cycle 1 Day 1; Cycle 1 Day 3; and Cycle 1 Day 8 only, for complete evaluation of tumor lysis.

Day 3 of Cycle 1

- Serum chemistries/liver function tests and phosphorus
- Evaluate for adverse events

Days 8 and 15 of Cycle 1 (+/- 3 days)

- Evaluate for adverse events
- Hematology
- Serum chemistries/liver function tests and phosphorus

Day 10 of Cycles 2-8 (+/- 3 days)

- Hematology
- Evaluate for adverse events

End-of-Treatment (End of Cycle 8) Visit

- Evaluate for adverse events
- Interval medical history including transfusion history
- Current medications
- Physical exam, including measurement of spleen, weight, and vital signs
- ECOG performance Status
- MPN-SAF modified for mast cell symptoms
- Hematology, chemistries/liver function tests, serum tryptase, PT, PTT (**Please refer to section 4.8.1 for detailed lab evaluations**)
- Pregnancy test (women of child bearing potential)
- MRI or CT of abdomen/pelvis with and without contrast including 3D spleen and liver volumes
- Chest x-ray 2 views - PA and lateral (only if disease related finding(s) were found at baseline)
- Bone marrow aspirate and biopsy with cytogenetics, flow cytometry, *KIT* mutation status
- Response assessment per IWG-MRT-ECNM criteria Drug Accountability

End of Study (EOS) Visit - if no response to the study drug after 8 cycles of treatment, one follow-up visit about 30 days after the end-of-treatment visit

- Evaluate for adverse events

- Interval medical history including transfusion history
- Current medications
- Physical exam, including measurement of spleen, weight, and vital signs
- ECOG performance status
- MPN-SAF modified for mast cell symptoms
- Hematology, chemistries/liver function tests, serum tryptase (**Please refer to Section 4.8.1 for detailed lab evaluations**)
- Pregnancy Test (women of child bearing potential)
- Response assessment per IWG-MRT-ECNM criteria

Follow-up visits - if patient did exhibit a response to the study drug after 8 cycles of treatment according to protocol response criteria, follow-up visits and labs every 6 weeks until 48 weeks from beginning of treatment will occur, then every 12 weeks.

- Evaluate for adverse events
- Interval medical history including transfusion history
- Current medications
- Physical exam, including measurement of spleen, weight, and vital signs
- ECOG performance status
- MPN-SAF modified for mast cell symptoms
- Hematology, chemistries/liver function tests, serum tryptase (**Please refer to Section 4.8.1 for detailed lab evaluations**)
- Bone Marrow aspirate and biopsy, cytogenetics, flow cytometry, *KIT* mutation status (at week 48, then every 24 weeks)
- MRI or CT of abdomen/pelvis with and without contrast including 3D spleen and liver volumes (at week 48, then every 24 weeks)
- Drug accountability
- Response assessment per IWG-MRT-ECNM criteria

Re-Staging if Loss of Response (LOR) (Day -21 to Day -1)

- Interval medical history including transfusion history
- Current medication list
- Physical exam with spleen measurement
- ECOG performance Status
- Vital signs (temperature, heart rate, breathing rate, blood pressure, weight)

- Magnetic resonance imaging (MRI) or computed tomography (CT) scan of the abdomen/pelvis with and without contrast including 3D spleen and liver volumes
- Bone marrow aspirate and biopsy with cytogenetics, flow cytometry, *KIT* mutation status
- Chest x-ray (2 views – PA and lateral)
- MPN-SAF modified for mast cell symptoms
- Hematology, chemistries/liver function tests, serum tryptase, **(Please refer to section 4.8.1 for detailed lab evaluations)**
- Pregnancy test (women of child bearing potential)
- Evaluate for adverse events

Re-Treatment Cycles 9 – 16 for patients who exhibit loss of response

- Repeat schedule of original cycles 1, and 2-8 except coags

End-of-Re-treatment (End of Cycle 16) Visit

- Evaluate for adverse events
- Interval medical history including transfusion history
- Current medications
- Physical exam, including measurement of spleen, weight, and vital signs
- ECOG performance Status
- MPN-SAF modified for mast cell symptoms
- Hematology, chemistries/liver function tests, serum tryptase, PT, PTT **(Please refer to section 4.8.1 for detailed lab evaluations)**
- Pregnancy test (women of child bearing potential)
- MRI or CT of abdomen/pelvis with and without contrast including 3D spleen and liver volumes
- Chest x-ray (2 views-PA and lateral) (only if disease related finding(s) were found at re-staging)
- Bone marrow aspirate and biopsy with cytogenetics, flow cytometry, *KIT* mutation status
- Response assessment per IWG-MRT-ECNM criteria
- Drug Accountability

End of Study (EOS) Visit - if no response to the study drug after 16 cycles of treatment, one follow-up visit about 30 days after the end-of-treatment visit should be undertaken. This is identical to the EOS visit for non-responders at the end of C8

Follow-up visits - if patient did exhibit a response to the study drug after 16 cycles of treatment according to protocol response criteria, follow-up visits and labs every 6 weeks until 48 weeks from beginning of re-treatment. Then every 12 weeks.

- Evaluate for adverse events

- Interval medical history including transfusion history
- Current medications
- Physical exam, including measurement of spleen, weight, and vital signs
- ECOG performance Status
- MPN-SAF modified for mast cell symptoms
- Hematology, chemistries/liver function tests, serum tryptase (**Please refer to section 4.8.1 for detailed lab evaluations**)
- Bone Marrow aspirate and biopsy, cytogenetics, flow cytometry, *KIT* mutation status (at week 48 from day 1 of re-treatment, then every 24 weeks)
- MRI or CT of abdomen/pelvis with and without contrast including 3D spleen and liver volumes (at week 48 from re-treatment, then every 24 weeks)
- Response assessment per IWG-MRT-ECNM criteria

There will not be any additional treatments after completion of the drug infusion at start of cycle 16. Patient will come for follow up visits per the schedule above as long as they show response. At the time of loss of response, patient will have an end of study visit (with the same assessments as at the end of study (EOS) visit for patients with no response at end of cycle 8 or 16) and will be taken off the study.

Long-term survival:

All patients will be followed every 6 months for survival until study closure or death of the patient.

Table 2. Visit and Assessment Schedule

	Screen	Assessments within +/- 3 days						End of Treatment (EOT) (@ completion of 8 cycles of therapy)	Day +30 after EOT for non-responders (g)	Maintenance labs and visits after 8 cycles for ongoing responders (h)	Re-Staging for pts who exhibit loss of response (LOR)	Re-Treatment Cycles 9-16 ^(a) for pts who exhibit loss of response (LOR)	Long Term Survival ^(j)
		Cycle 1			Cycle 2-8								
Evaluation	Day -28 to Day -1	Day 1 ^(b)	Day 3 (can be local)	Day 8 (can be local)	Day 15 (can be local)	Day 1	Day 10 (can be local)	(EOT)	(EOS)	Labs and visits q 6 weeks up to week 48; then q 12 weeks	Day -21 to Day -1	Repeat schedule of original cycles 1, 2-8 and EOT (except PT, PTT)	
Informed consent/eligibility criteria	X												
Complete medical history	X												
Interval medical history		X				X		X	X	X	X		
Prior and concomitant medications	X	X				X		X	X	X	X		
Transfusion history in prior 12 weeks	X	X				X		X	X	X	X		
Vital signs, physical exam, body weight, height ⁽ⁱ⁾	X ⁽ⁱ⁾	X				X		X	X	X	X		
ECOG performance status	X	X				X		X	X	X	X		
MPN-SAF, QOL questionnaires	X	X				X		X	X	X	X		
12-lead ECG	X												
Hematology ^(c)	X	X		X	X	X	X	X	X	X	X		
Serum chemistries/liver function tests ^(c)	X	X	X	X	X	X		X	X	X	X		
Serum tryptase level	X	X				X		X	X	X	X		
PT and PTT	X	X				X		X					
Pregnancy test	X	X				X		X	X		X		
Chest x-ray (2 views-PA and Lateral) ^(d)	X					X ^(d)		X ^(d)			X		
BM aspiration, cytogenetics, flow cytometry, core biopsy, and KIT mutation analysis ^(e)	X					X ^(e)		X ^(e)		X ^(e)	X		
MRI (or CT) abdomen/pelvis with and without contrast including 3-D spleen and liver volumes ^(f)	X					X ^(f)		X ^(f)		X ^(f)	X		
Measurement of spleen by palpation	X	X				X		X	X	X	X		
Drug accountability assessment		X				X		X		X			

A study of brentuximab vedotin (SGN-35) in CD30-positive systemic mastocytosis with or without an associated hematological clonal non-mast cell lineage disease (AHNMD)

Administer study drug during visit		X				X							
Record Adverse Events		X	X	X	X	X	X	X	X	X	X		
Response assessment per IWG-MRT-ECNM Criteria						X		X	X	X			

- a For patients demonstrating loss of response (LOR) after completion of 8 cycles of therapy, re-treatment for up to an additional 8 cycles (eg, cycles 9-16) may be undertaken. Before re-treatment, **patients should undergo all re-staging studies as shown in the initial screening period, except that a 12-lead EKG and coagulation studies (PT and PTT) are not required. The re-staging period should be completed within 21 days (+/- 3 days) between identifying a loss of response (LOR) and re-initiating treatment. Cycles 9-16 study drug administration and labs/procedures will be conducted on a schedule identical to cycles 1 and 2-8 with an end of treatment (EOT) visit at the completion of cycle 16 of therapy except PT and PTT which will NOT be performed with cycles 9-16, end of treatment (EOT) visit at the completion of cycle 16, or the end of study (EOS) visit.**
- b Day 1 labs do not need to be repeated if obtained during screening within 72 hours of day 1. Patient infusion on cycle 1, day 1 as well as additional cycles will occur in an outpatient infusion center.
- c Refer to section 4.8.1 for the labs that should be obtained for hematology and chemistries/liver function tests.
- d If disease-related findings are found on chest x-ray (2 views PA and lateral) (eg, pleural effusion), then an x-ray will be performed at the end of cycles 4 and 8 or EOT, whichever comes first, and at the time of progressive disease or loss of response (LOR). Chest X-ray (2 views-PA and lateral) will also be performed at the time of re-staging. If disease-related findings are found on chest x-ray (eg, pleural effusion) at the time of re-staging, then an x-ray will be performed at the end of cycles 12 and 16 or EOT, whichever comes first, and at the time of progressive disease or loss of response (LOR). Interval chest x-rays can be performed at the discretion of the investigator.
- e Besides screening, marrows will be performed at the end of cycles 4 and 8 or EOT, whichever comes first, and at the time of progressive disease or loss of response (LOR). A repeat bone marrow aspirate and biopsy should be performed at the end of week 48 and every 6 months thereafter in ongoing responders. Please refer to section 4.9 Central Histopathology Review for items required with bone marrow biopsy and aspiration.
- f MRI (or CT scan) abdomen/pelvis with and without contrast including 3-D spleen and liver volumes will be obtained at screening, at the end of cycle 4, and at the end of cycle 8 or EOT, whichever comes first, and at the time of progressive disease or loss of response (LOR). Interval MRI or CT scans can be performed at the discretion of the investigator. A repeat MRI or CT should be performed at the end of week 48 and every 6 months thereafter in ongoing responders.
- g A visit on day +30 will be conducted after the EOT visit for follow-up for non-responders. This will be end of study visit (EOS)
- h After 8 cycles of therapy are completed, labs and visits with the trial site every 6 weeks up to week 48; then every 12 weeks.
- i Height is to be obtained only at screening.
- j Long Term Survival: every 6 months after end of study visit until study closure or death of the patient.

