3.2 Discussion of design

Patients will receive open label SGN-35 at a starting dose of 1.8 mg/kg administered as a single IV infusion as on Day 1 of each 21-day cycle as an outpatient. Patients will be treated for eight 21-day cycles. The best response per international response criteria will be recorded by the end of cycle 8. Because responses must last at least 12 weeks, any clinical improvement (CI), partial response (PR), or CR response that commences by the end of cycle 8, and either persists or evolves into a higher quality response for at least 12 weeks will be counted as a response. Patients who demonstrate a response and subsequently meet criteria for loss of response (LOR) will be permitted to undergo re-staging and re-treatment with up to an additional 8 cycles of SGN-35.

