4.3 Treatment Discontinuation

Any patient discontinuing study medication prematurely must have the reason categorized on the CRF as one of the following:

1. adverse event(s)
2. abnormal laboratory value(s)
3. abnormal test procedure result(s)
4. unsatisfactory therapeutic effect
5. subject's condition no longer requires study treatment
6. protocol violation
7. subject withdrew consent
8. lost to follow-up
9. administrative problems
10. death

Patients who discontinue the study due to a study drug-related adverse event must be followed weekly for four weeks, or until resolution or stabilization of the event, whichever occurs first.

Patients discontinuing prematurely are to be followed every 6 months for survival until study closure or death of the patient.

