7.6.5 Progression-free survival (PFS) and overall survival

Progression-free survival (PFS) is defined as the time from the date of start of treatment until the date of first documented confirmed disease progression or death or institution of new therapy. If a patient did not progress or die due to any cause at the time of the analyses, PFS will be censored at the date of the last adequate response assessment. Kaplan-Meier product-limit estimates will be used to summarize PFS. For overall survival, patients will be contacted every 6 months until the study closure or death.

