APPENDIX G Contd.:

APPENDIX G: WG-MRT-ECNM consensus response criteria for patients with ASM, MCL, and SM associated with a myeloid neoplasm

Complete remission (CR)*

Requires all 4 criteria and response duration must be ≥ 12 wk

No presence of compact neoplastic mast cell aggregates in the BM or other biopsied extracutaneous organ

Serum tryptase level < 20 ng/mL†

Peripheral blood count remission defined as ANC $\geq 1 \times 10^9/L$ with normal differential, Hb level ≥ 11 g/dL, and platelet count $\geq 100 \times 10^9/L$

Complete resolution of palpable hepatosplenomegaly and all biopsy-proven or suspected SM-related organ damage (CI findings)‡

Partial remission (PR)*

Requires all 3 criteria and response duration must be ≥ 12 wk, in the absence of both CR and progressive disease (PD)

Reduction by $\geq 50\%$ in neoplastic MCs in the marrow and/or other extracutaneous organ at biopsy demonstrating eligible SM-related organ damage

Reduction of serum tryptase level by $\geq 50\%$ †

Resolution of 1 or more biopsy-proven or suspected SM-related organ damage (CI finding(s)) ‡

Clinical improvement (CI)*

Response duration must be ≥ 12 wk

Requires 1 or more of the nonhematologic and/or hematologic response criteria to be fulfilled (see Table 3) in the absence of both CR/PR assignment or progressive disease (PD)

Stable disease (SD)

Not meeting criteria for CR, PR, CI, or PD

Progressive disease (PD)§

Requires at least 1 element of either criteria 1 or 2 and duration must be ≥ 8 wk

(1) For patients with baseline grade 2 nonhematologic organ damage: a) worsening by 1 grade, AND b) minimum 100% increase (doubling) of laboratory abnormality.

For patients with baseline \geq grade 2 albumin: (a) worsening by 1 grade, AND (b) decrease by ≥ 0.5 g/dL.

For patients with baseline \geq grade 3 nonhematologic organ damage: minimum 100% increase (doubling) of laboratory abnormality.

For patients with baseline \geq grade 2 transfusion-independent anemia or thrombocytopenia: New transfusion dependence of ≥ 4 units of RBCs or platelets at 8 wk.

For patients with baseline transfusion-dependent anemia or thrombocytopenia: $\geq 100\%$ increase in the average transfusion frequency for an 8-wk period compared with the 12-wk pretreatment period

For patients with baseline grade \geq grade 3 neutropenia: (a) $> 50\%$ decrease in neutrophil count, AND (b) absolute decrease of neutrophil count of $\geq 250/mm^3$, AND c) grade 4

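### In non-responders, laboratory- or spleen-based progression first seen from about Cycle 8, or near an early stop, cannot meet the 8-week rule on schedule, which biases PFS upward

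*Combined protocol and SAP*

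**What the plan says.** **Event and censoring.** Section 7.6.5 runs PFS from start of treatment "until the date of first documented confirmed disease progression or death or institution of new therapy". Without progression or death, "PFS will be censored at the date of the last adequate response assessment". Section 2.3.2 defines the event the same way.

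**Progression.** Appendix G: "Requires at least 1 element of either criteria 1 or 2 and duration must be ≥ 8 wk".

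**Treatment and assessment.** Section 3.2: "Patients will be treated for eight 21-day cycles". Section 4.6.1 assesses response on Day 1 of each cycle from Cycle 2, and at EOT.

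**Non-responders.** Section 4.6.1 then provides, "if no response to the study drug after 8 cycles of treatment, one follow-up visit about 30 days after the end-of-treatment visit". Table 2 note g makes this their end-of-study visit. After it, only 6-monthly survival contact is scheduled (Section 4.6.1; Table 2 note j).

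**Responders.** Visits with response assessment continue every 6 weeks to week 48, then every 12 weeks (Section 4.6.1).

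**Early stoppers.** Section 4.3: "Patients discontinuing prematurely are to be followed every 6 months for survival until study closure or death of the patient". Table 2 notes d to f allow EOT to fall before the end of cycle 8 and call for tests at progressive disease. Note g does not limit the day +30 visit to patients who completed 8 cycles. Section 4.8.1 asks for imaging, if feasible, when a patient leaves before the end of cycle 4.

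**The concern.** A 30-day tail cannot satisfy a 56-day duration rule. A non-responder whose worsening is first seen late in treatment leaves scheduled assessment before it can qualify as progression. Under Section 7.6.5 that patient is censored, or becomes an event only at a later death or new therapy. The plan solves the matching problem for response: Section 4.7.1 keeps patients whose response starts in cycles 6 to 8 on 6-weekly visits so that 12 weeks can be observed. Late progression has no such provision.

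PFS is a stated secondary objective (Section 2.2). At the 10% to 30% response rates in Section 7.8, non-responders make up 70% to 90% of patients, or about 8 to 10 of 11. Whether disease follow-up continues depends on response status, so the censoring is informative. With so few patients, a handful of missed or late-dated events can move the Kaplan-Meier curve.

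**Working it through.** **The plan's own figures.** The documents give no design figure for PFS. The only one is for the response rate: continue with at least 2 of 11, succeed with at least 5 of 26. The probability of success is the sum over x = 2 to 11 of P(X1 = x) × P(X2 ≥ 5 − x), with X1 binomial on 11 and X2 on 15. This gives 0.0865 at a 10% rate and 0.8516 at 30%. Early stopping is 0.697 and 0.113. All match Section 7.8 (8.7%, 85%, 70%, 11%). None of these depends on how progression is confirmed.

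**Calendar for a non-responder completing 8 cycles.** Inputs: 21-day cycles, first dose on day 1, no dose delays. Cycle k Day 1 is day 1 + 21(k − 1), EOT is day 169, and EOS is day 169 + 30 = 199. The duration rule is 8 × 7 = 56 days.

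| Progression first seen | Day | Days left to EOS | First visit at least 56 days later |
|---|---|---|---|
| Cycle 2 Day 1 | 22 | 177 | Cycle 5 Day 1 |
| Cycle 3 Day 1 | 43 | 156 | Cycle 6 Day 1 |
| Cycle 4 Day 1 | 64 | 135 | Cycle 7 Day 1 |
| Cycle 5 Day 1 | 85 | 114 | Cycle 8 Day 1 |
| Cycle 6 Day 1 | 106 | 93 | EOT |
| Cycle 7 Day 1 | 127 | 72 | EOS |
| Cycle 8 Day 1 | 148 | 51 | none |
| EOT | 169 | 30 | none |
| EOS | 199 | 0 | none |

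Six of nine assessments leave time to confirm. Cycle 8 Day 1 is 5 days short. If that visit is 3 days early and EOS 3 days late, the gap is 51 + 6 = 57 days, which is enough.

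**Early stoppers** (EOT assumed at the end of the last cycle given):
- With EOT and a day +30 visit, no assessment is confirmable after stopping in cycle 1 or 2. After cycles 3 to 7, 1 of 4, 2 of 5, 3 of 6, 4 of 7 and 5 of 8 are.
- With EOT only, none is confirmable after cycles 1 to 3. After cycles 4 to 7, 1 of 4, 2 of 5, 3 of 6 and 4 of 7 are.
- On either reading, progression first seen at an early EOT visit has at most 30 days left.

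**Size.** The latest onset that EOS can confirm is day 199 − 56 = 143. Assume exponential time to progression, with S(t) = 2^(−t/median). The medians are assumptions.

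| Median | S(143) | S(199) | Onset days 143–199, share of all | Same, share of onsets by EOS | Onset after EOS, share of all |
|---|---|---|---|---|---|
| 3 months (91 d) | 0.34 | 0.22 | 12% | 15% | 22% |
| 6 months (183 d) | 0.58 | 0.47 | 11% | 21% | 47% |
| 12 months (365 d) | 0.76 | 0.69 | 8% | 24% | 69% |

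The fourth column is S(143) − S(199). The fifth divides it by 1 − S(199). Only the fourth and fifth columns are due to the 8-week rule; the last reflects the end of disease follow-up.

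If duration runs from the visit where progression is first seen, the cut-off moves back to Cycle 7 Day 1. The unconfirmable share of onsets by EOS is then 20%, 28% and 32% for medians of 12, 26 and 52 weeks.

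**The case against.** Much can be said for the plan as written.

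- **Most assessments are confirmable.** Completers are seen every 3 weeks, and six of nine assessments leave time to confirm. A reader might infer that most progressions in non-responders can never become PFS events. The documents do not support that. They give no progression rate, and the 3-month case above contradicts it. Death and new therapy are also PFS events. This stands, except that no collection of new-therapy dates is scheduled after EOS.
- **The 8-week rule is only part of the loss.** A reader might attribute everything after day 143 (34%, 58%, 76%) to it. Most of that is progression starting after EOS, missed because disease follow-up ends. This stands.
- **Not every form of progression is equally affected.** The transfusion-based elements in Appendix G use their own 8-week period, and Table 2 collects 12-week transfusion history at EOT and EOS, so they can be documented by look-back. Transformation to AML is listed separately as progression. This stands and confines the point mainly to laboratory and spleen findings.
- **Early stoppers.** Section 4.3 might be read as moving them to survival contact alone. It does not say that, and Table 2 and Section 4.8.1 point to further assessments. What stands is that the passages do not agree clearly.
- **Stopping at first progression.** A reader might suppose that patients stop treatment when worsening is first seen, so that almost none could be confirmed. The protocol states no such rule, and under Appendix G a worsening is not yet progression until 8 weeks have passed.
- **Limited consequence.** PFS is a descriptive summary in a single arm of 11 patients, or 26 by amendment, with no PFS test or decision rule. This stands and limits the weight of the point.

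**Conclusion.** The structural gap is real. In non-responders, laboratory- or spleen-based progression first seen at EOT or EOS cannot be confirmed on schedule. At Cycle 8 Day 1 it can be confirmed only if visit windows fall favourably. Progression first seen near an early stop has the same problem, and progression after about day 199 is not looked for. Because the patient is censored or the event is dated later, PFS in non-responders is biased upward, while responders keep 6- to 12-weekly assessments.

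Under assumed medians of 3, 6 and 12 months, the 8-week rule costs about 15%, 21% and 24% of progressions starting by EOS, and 22%, 47% and 69% of all progressions start afterwards. These figures rest on exponential onset, no dose delays and nominal visit dates.

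One qualification on direction: the upward bias is clear up to EOS and for any patient whose event is dated at death instead of progression. Beyond EOS, living non-responders leave the risk set at their last assessment while deaths still count, which pulls the tail of the curve the other way. I have not quantified this.

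The point concerns a secondary endpoint only, and changing the plan is advisable because the remedy is cheap.

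**What to change.** 1. **Section 4.6.1 and Table 2 note g.** For non-responders with progression first seen at Cycle 8 Day 1 or at EOT, time the existing EOS visit at least 56 days after that finding. Nominally this is day 148 + 56 = 204 or day 169 + 56 = 225 instead of 199, so 5 or 26 days later.
2. **6-monthly survival contact.** Also record the dates of progression and of new therapy. New therapy is already a PFS event, and nothing scheduled after EOS captures it.
3. **Section 7.6.5.** Keep confirmed progression for the main PFS analysis. Add a sensitivity analysis that counts unconfirmed progression on its first documented date when follow-up ended before 8 weeks. Require that no later assessment reverses it and that the Appendix G guideline on excluding drug toxicity and other causes (guideline 4) is met. Using this as the main definition is debatable, because it would mix confirmed and unconfirmed events and depart from the adopted criteria.
4. **Early stoppers.** Reconcile Section 4.3 with Table 2 notes d to g and Section 4.8.1, stating which EOT and day +30 assessments these patients receive.

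Cost: protocol and analysis-plan wording, a later visit for a few patients, and two items at an existing contact. Reported PFS will probably be shorter.

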2.3.2 Secondary Efficacy Endpoints

- Immunohistochemical expression of CD30 on neoplastic mast cells in core biopsy samples or by flow before SGN-35 treatment and after 4 and 8 cycles of therapy
- Total symptom score and QOL score using a modified Myeloproliferative Neoplasm Symptom Assessment Form (MPN-SAF)
- Duration of response (DoR) is defined as the time from first onset of confirmed response to the date of first documented and confirmed progression or death due to ASM/MCL. Time to response (TTR) is defined as the time from start of treatment until the date of onset of a confirmed response
- Progression-free survival (PFS) is defined as the time from start of treatment to the date of the first documented and confirmed progression or death or institution of new therapy

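### PFS counts the start of new therapy as an event, but no new-therapy date is scheduled for collection after the end-of-study visit and the censoring sentence omits it, so PFS beyond that visit cannot be computed as defined

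*Combined protocol and SAP*

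**What the plan says.** The endpoint list (2.3.2) runs PFS from start of treatment to "the date of the first documented and confirmed progression or death or institution of new therapy". The statistical section (7.6.5) repeats the three events: "date of first documented confirmed disease progression or death or institution of new therapy".

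The censoring sentence in 7.6.5 names only two of them: "If a patient did not progress or die due to any cause at the time of the analyses, PFS will be censored", with the censoring date set at the last adequate response assessment.

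While patients attend visits, therapy is documented. Section 4.6.1 lists current medications at each cycle, at end of treatment, at EOS, at responder follow-up and at re-staging. Section 4.4 requires all concomitant therapies on a CRF.

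For non-responders, visits end about 30 days after end of treatment. For responders who are not re-treated again, they end at loss of response. What follows is described in the same way in three places:

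- 4.6.1, Long-term survival: "All patients will be followed every 6 months for survival until study closure or death of the patient".
- 4.3, for early stoppers: "Patients discontinuing prematurely are to be followed every 6 months for survival until study closure or death of the patient".
- Table 2, footnote j: "Long Term Survival: every 6 months after end of study visit until study closure or death of the patient".

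Section 7.6.5 gives overall survival as the purpose of this contact. Section 4.4 bars other anti-cancer agents during the study, with an exception for hydroxyurea.

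**The concern.** One of the three PFS components has no scheduled data source in the period when it is most able to occur. Because other anti-cancer treatment is barred on study, most new therapy can start only after a patient leaves. Section 1.1 describes patients with aggressive disease as candidates for cytoreductive or targeted treatment, so some who do not respond to SGN-35 can be expected to receive something else.

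There is a second, linked defect. A patient who has started a new therapy without progressing is an event under the definition but is censored under the censoring sentence, even when the date is known. Analysts following the same text could produce different PFS curves.

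At stake is whether the reported PFS measures what its definition says. A date not asked for at the time may be hard to recover later.

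**Working it through.** **Text check.** The plan gives no PFS figure (no assumed median, event count or rate), so there is nothing of its own to reproduce. For each event, the source after EOS or early discontinuation is:

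- Death: the 6-monthly contact.
- Progression: no response assessment is scheduled.
- New therapy: no item is scheduled.

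A death counts as an event whenever it occurs. A survivor without recorded progression goes back to the last response assessment.

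**Illustration of direction.** Every rate here is an assumption.

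- 30% are responders who stay under assessment and start no new therapy; 70% are non-responders.
- Non-responders reach EOS at 8 × 21 + 30 = 198 days, or 6.5 months.
- From EOS, non-responders start new therapy at exponential times with median m months.
- Death is exponential for everyone with median d months, so S(t) = 2^(−t/d).
- Closure is at 24 months, with no progression.

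Full definition at 12 months (12 − 6.5 = 5.5 months after EOS):

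PFS = S(12) × [0.30 + 0.70 × 2^(−5.5/m)]

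Rules as written: non-responders alive at closure are censored at EOS, so the later risk set holds living responders plus only those non-responders who will die before closure:

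PFS = S(6.5) × {1 − [S(6.5) − S(12)] / [0.30 S(6.5) + 0.70 (S(6.5) − S(24))]}

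The second formula does not contain m: the reported curve does not react to new therapy at all.

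- d = 12: S = 0.687, 0.500 and 0.250 at 6.5, 12 and 24 months. Risk set 0.206 + 0.306 = 0.512. PFS = 0.687 × (1 − 0.187/0.512) = 0.436.
- d = 36: S = 0.882, 0.794 and 0.630. Risk set 0.265 + 0.177 = 0.441 (from unrounded terms). PFS = 0.882 × (1 − 0.089/0.441) = 0.705.
- Full definition, d = 36 and m = 2: 0.794 × (0.30 + 0.70 × 0.149) = 0.321. The other rows follow in the same way.

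| Median survival d | Median to new therapy m | Full definition | As written | Difference |
|---|---|---|---|---|
| 12 | 2 | 0.202 | 0.436 | +0.23 |
| 12 | 8 | 0.367 | 0.436 | +0.07 |
| 36 | 2 | 0.321 | 0.705 | +0.38 |
| 36 | 8 | 0.583 | 0.705 | +0.12 |
| 36 | 24 | 0.712 | 0.705 | −0.01 |
| 36 | 60 | 0.760 | 0.705 | −0.05 |

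The sign changes because staying in the risk set after EOS depends on dying later. Known survivors are removed at EOS while their counterparts' deaths are kept, which pulls the curve down.

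**Effect of progression.** Adding progression with an assumed 6-month median (counted in both versions, and for non-responders only up to EOS) and simulating the first four rows shrinks the gap to about 0.5 to 13 points. With a 4-month median it is about −1 to +8 points.

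**Would collecting the dates be enough?** Take d = 36, m = 60, and leave survivors censored at the last assessment.

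- Combined hazard: ln 2 × (1/36 + 1/60) = 0.0308 per month.
- Non-responders alive at EOS: 0.70 × 0.882 = 0.618.
- Fraction of these with an event by closure: 1 − exp(−0.0308 × 17.5) = 0.417, which is 0.257 of all patients.
- Risk set: 0.265 + 0.257 = 0.522.
- Events between EOS and 12 months: 0.30 × 0.089 + 0.618 × 0.156 = 0.123.
- PFS = 0.882 × (1 − 0.123/0.522) = 0.675, against 0.760 under the full definition: about 9 points too low.

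The dates and the censoring sentence must be corrected together.

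**The case against.** **Earlier starts are captured.** A reader might infer that new-therapy dates are never collected. The documents do not support that: medications are recorded at every visit up to and including EOS, and responders are seen until loss of response. The gap begins after EOS or premature discontinuation. This limits the point but does not remove it.

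**Overstatement is not shown.** A reader might infer that PFS is overstated, and by a definite amount. Patients are not carried forward as event-free; they are censored at the last assessment. As the table shows, the sign depends on rates the plan does not give, and the largest gaps need both early new therapy and no progression. Section 1.1 also notes that options for aggressive disease are limited, so rapid uptake of another treatment cannot be taken for granted. This objection stands in full.

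**The empty column in Table 2 proves little.** The Long Term Survival column has no marks, but the table has no survival-status row, and the re-treatment column is blank although all its procedures repeat. The survival CRF is not in the documents. The argument therefore rests on the wording of 4.3, 4.6.1, footnote j and 7.6.5, all of which describe this contact as being for survival.

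**A date may not be needed.** If PFS were confined to the assessed period and later deaths excluded, no post-EOS therapy date would be required. That is a coherent alternative, but it is not what 2.3.2 and 7.6.5 define.

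**The impact is limited.** PFS is a Kaplan-Meier summary with no hypothesis attached, in a first stage of 11 patients. This bears on priority, not on whether the text is consistent.

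**Conclusion.** The point holds on the text alone. PFS includes new therapy as an event, no new-therapy date is scheduled for collection after EOS or early discontinuation, and the censoring sentence disagrees with the definition. PFS beyond EOS cannot be computed as written.

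The direction of any bias is conditional: probably upward if new therapy soon follows EOS, downward if it is slow or rare. Across the scenarios shown, the 12-month difference runs from +38 to −5 points without progression, and is about 0.5 to 13 points in the early-therapy scenarios once a 6-month median progression is added. These figures rest wholly on assumed exponential rates, 30% responders and closure at 24 months. They illustrate a mechanism and are not an estimate for this trial.

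The two-stage decision in 7.8 uses response rate only and is unaffected. The change should be made because it is cheap and the dates may be hard to recover afterwards.

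**What to change.** - **Collection.** In 4.3, 4.6.1 (Long-term survival), Table 2 and footnote j, define the existing 6-monthly contact as recording survival status plus the date and type of the first new mast-cell-directed or anti-neoplastic therapy, and mark these items in the Long Term Survival column.
- **Derivation.** In 7.6.5, count that date as a PFS event and extend the censoring condition to patients who did not progress, die or start new therapy.
- **Late deaths.** State in 7.6.5 how deaths after the last response assessment are handled, so that late deaths are not counted as events while comparable survivors are censored back at that assessment without explanation.
- **Limitation.** State in 7.6.5 that progression is not assessed after EOS, so PFS after that visit rests on death and new therapy only.

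Cost: one question and two CRF fields at a contact that already takes place, with no extra visit or procedure. Reported PFS may become less favourable.
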